3.7 Inclusion and Exclusion criteria

The following lists outline key criteria used by the principal investigator, sub-investigators, and study team to determine who can and cannot be in this study.

Inclusion Criteria

1. Males and females between the ages of 18 and 80 (inclusive) with ulcerative colitis-associated IPAA with and without pouchitis
2. Eligible patients will be identified through the Emory Clinic (TEC), St. Joseph's Hospital (SJH), and Emory University Hospital (EUH)
3. Signed informed consent

Exclusion Criteria

1. Age <18 years or >80 years of age
2. Exposure to immunosuppressive therapy within the 4 weeks prior to enrollment or their expected use within 1 month of FMT
3. Concomitant *Clostridium difficile* infection
4. Suspected Crohn's disease
5. Documented active infection of any kind
6. Patients on anti-coagulant therapy, with platelet count less than 50,000, significant anemia with hemoglobin < 7, or those with other conditions that place them at increased risk of bleeding
7. Pregnant or breastfeeding women (pregnancy will be verified using urine pregnancy kits)
8. Need for imminent surgery
9. Absolute neutrophil count (ANC) < 1000 or history of opportunistic infection
10. Administration of any investigational drug within one month before FMT

Demographic data, including prior history of pouchitis with sub-classification into chronic antibiotic resistant (refractory) pouchitis, chronic antibiotic use as well as previous treatments will be recorded. Measures of waist and hip circumference and waist to hip ratio will be calculated and recorded. Stool samples, urine, and serum samples will be collected. Patients will be screened at entry for enteric pathogens (*C. difficile*, routine bacterial stool culture, ova and parasites) and positive results will exclude entry to the study.

Fecal samples from subjects will be analyzed for microbiome genetics, and metabolomic profiles before and four weeks after therapy. Scored symptoms according to the modified pouch disease activity index (mPDAI) (**Appendix 1**) as proposed by Shen et al. will also be recorded.

FMT in UC-associated Pouchitis
Version 3.0, date finalized 06/26/2017

documented before pouch endoscopy. Investigation with biopsy incorporating both endoscopic and histologic criteria will be pursued. As per Shen's protocol when developing the modified PDAI (mPDAI), biopsies will be taken from the posterior wall of the pouch if the pouch has abnormal endoscopic appearance and from areas of maximal inflammation (Shen 2003). In addition to the two to four biopsies that are taken for the pathologist, additional biopsies will be taken to study the epithelial microbiome.

No more than 6 total biopsies will be taken. A single gastrointestinal pathologist, blinded to the clinical presentations and endoscopic findings, will assess the pouch biopsies for grade of inflammation. On the basis of the criteria proposed by Sanborn et al patients with a total PDAI of seven or more will be classified as having pouchitis. Symptomatic patients without endoscopic and histologic evidence of pouchitis and a PDAI less than seven points will be defined as not having pouchitis. All patients undergoing pouchoscopy will receive a universal donor fecal transplant deposited in the most proximal limit of the afferent limb after the mucosal biopsies are obtained. There will be 2 categories of patients. Patients with pouchitis symptoms with endoscopic and histologic evidence of pouchitis, and patients with pouchitis symptoms without endoscopic features, but with histologic evidence of pouchitis.

We will assess patient perceived improvement in symptoms and quality of life by asking participants to complete two surveys--Short Quality of Life Questionnaire for Inflammatory Bowel Disease and the Cleveland Global Quality of Life. Participants will be asked to complete these surveys at enrollment and again at 4 weeks and 12 weeks post-FMT procedure (**Appendix 4**).

4. BIOLOGICAL SPECIMENS TO BE ACQUIRED

1. *Fecal sample*- The patient will submit a stool specimen in a container for genomic analysis at week 0, week 2, week 4, and week 12. Prior to enrollment, the patients will undergo PCR testing for *C. difficile*, routine stool culture, and ova and parasites. Any remaining stool sample will be used for research purposes for microbiota evaluation by 16S sequencing.
2. *Mucosal Pouch Tissue* -A total of up to 6 mucosal biopsies will be taken during routine standard of care flexible sigmoidoscopy procedure in patients undergoing investigation for presumed pouchitis or for routine surveillance of the pouch in patients without pouchitis. Two to four will be sent to pathology for assessment of histology. Two to four biopsies will be obtained for research purposes. No more than a total of 6 will be taken. All non-research biopsies will be placed in saline and transported to the Pathology Department at Emory immediately. Research related

biopsies will be collected by the study team and transported to the Pathology Department at Emory University.

3. *Stool*- Additional stool will be collected after treatment 4 weeks and 3 months after fecal microbial transplant (FMT). If the first and second study visit occur within 48hours, the second collection of biologic samples will be at the discretion of the study doctor.

Samples collected through this study will be given a de-identified code that is not derived from or related to information about the individual and is not otherwise capable of being translated to identify an individual. The samples will then be barcoded and transported to a central core laboratory at Emory University managed by [name]. Fecal and mucosal samples will be saved and stored in locked refrigerators/freezers in [name] laboratory in the Woodruff Memorial Building. DNA will be extracted for sequencing at this laboratory using automated extraction. Sequencing of the 16S regions will be performed in [name] laboratory.

Plasma and urine samples will be collected from each patient at study visits as illustrated in the study procedures table, and will be barcoded and saved in locked freezers in [name] laboratory in the Woodruff Memorial Building until all the samples are collected. At such time, they will be transported to [name] laboratory in the Whitehead building for metabolomic profiling.

Biological samples will not be collected on subjects who complete study visits via telephone follow-up.

5. ADDITIONAL DATA COLLECTION

Additional information will also be gathered from the patient's medical chart. This will include demographic information including age, sex and race, as well as clinical information such as pre-existing medical conditions, allergies, medicines prescribed, diseases that run in the patient's family, any previous surgical procedures, and the results of any previous medical testing (including biopsy results).

Subjects will be asked to complete a Food Recall Questionnaire at enrollment, week 4 and week 12 (**Appendix 5**).

Any data obtained from the patient's medical record will have any and all identifiable information removed and will be kept in a password protected electronic file accessible only

by the authorized study team.

6. REQUIRED NUMBER OF PARTICIPANTS

A total of 11 patients with IPAA/UC related pouchitis will be enrolled over 12 months as part of this pilot study.

7. PATIENT SAFETY

The risks of this study are limited to those inherent with mucosal tissue biopsy and fecal microbial transplant with use of a flexible sigmoidoscopy.

The primary risk associated with a mucosal tissue biopsy is bleeding from the area of biopsy. Significant bleeding from the biopsy site is uncommon, but possible (1 in 1,000). Even more rarely (1 in 3,000), a perforation can be made at the site of biopsy which would require surgery to repair. To minimize these risks, standard practice is to not take a biopsy of large vessel, not to repair.

To minimize these risks, standard practice is to not take a biopsy of large vessel, not more than one biopsy from a given mucosal site and not to over distend the bowel lumen while taking biopsies. Furthermore, mucosal biopsies are not painful as the bowel lining does not have pain fibers to sense pain. In addition, all the above mentioned risks apply regardless if the biopsy is done for donating tissue to this study or for diagnostic purposes. Mucosal biopsy sampling will be performed by medical staff with expertise in performing these procedures.

Research associated peripheral blood draws may result in some discomfort or risk of bruising at the site of the needle entry. There is a remote risk of fainting from a vasovagal response or local infection. These risks will be minimized using trained phlebotomists and aseptic technique. Sample collections will be performed with the patient seated or recumbent.

There is not significant risk to urine donation. There is not significant risk to stool donation.

The primary risks of fecal microbiota transplantation are transmission of infection and potential immune stimulation. We will be using a standard donor who will be screened for transmittable infections through serologic and stool testing. In addition, the donor will be screened clinically for illness in which there is potential for disruption of normal gastrointestinal flora such as irritable bowel syndrome. The donor will be excluded from the study if he is found to have such an illness. The risk associated with placement of the transplant enema through flexible sigmoidoscopy is discomfort. Small volume (100 mL-200mL) enemas will be used to minimize this risk.

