1. SPECIFIC AIMS

The aims of this study are: 1) to determine the utility of fecal microbiota transplantation (FMT) in the treatment of patients with ulcerative colitis (UC) associated chronic antibiotic-dependent pouchitis (CADP) and chronic antibiotic refractory pouchitis (CARP) and 2) to study the changes in the microbial environment in patients with pouchitis (pre- and post-treatment) and 3) to assess the impact of therapy on the patient's perceived quality of life.

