3. STUDY DESIGN

The primary investigative design will be a single arm study to determine if FMT has the potential to be used in the treatment of chronic pouchitis.

3.1 *Study Objectives:*

Primary Objective: To determine the safety and tolerability of fecal microbiota transplant (FMT) in treatment of chronic pouchitis

Secondary Objective: To study the microbial environment of IPAA/UC associated pouches in patients presenting with symptoms of pouchitis with and without endoscopy-visualized pouchitis and to assess the impact of the therapy on the patient's perceived quality of life

3.2 *Study design Type/Phase:* This is a two center, Phase 1 open label study designed to determine the safety, tolerability and use of fecal transplant in patients with pouchitis and to study the differences in microbiome in patients before and after treatment with FMT.

3.3 *Sites Centers of Research:* This study will be conducted in the Emory Clinic- Adult Digestive Disease Clinic and Colorectal Surgery Clinic, the Emory Center Endoscopy Center, and St. Joseph's Hospital (SJH) in Atlanta, GA.

3.4 *Measures to minimize/avoid bias:* Eligible subjects will be given options of other treatments if they choose not to participate.

3.5 *Study duration:* The total duration of the study for each patient will be twelve weeks.

3.6 *Study Procedures*

The following protocol essentially requires two sets of study procedures. One set of study procedures outlines testing requirements for the donor of allogenic human feces (see **Table 1.** Donor Related Study Activities). The other set outlines activities and expectations of the research participant who will receive the donated stool specimen (see **Table 2.** Research Participant Study Activities). The donor set of activities will be managed by [name], a sub-investigator and Associate Professor of Medicine within the Division of Infectious Diseases. In the past, [name] has overseen the donor recruitment and screening within previous FMT trials via ordering the appropriate antibody screens, fecal sample preparation (e.g. use of saline, etc.) and any other necessary tests to ensure that the fecal specimen is non-infectious and safe for insertion into research participants. [name] still oversees this process and prepares the allogenic human fecal FMT in UC-associated Pouchitis

Version 3.0, date finalized 06/26/2017

donation in her lab on site. However, she will not be able to provide these activities listed in **Table 1** for effort.

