- Biohazard containers for disposal of contaminated materials are readily accessible in the processing area.
- Good laboratory techniques will be exercised to minimize the formation of aerosols, droplets, spatters, splashes.

The FMT processing (performed by [name]) involves taking of the standard donor's stool which is received in the clinical microbiology laboratory along with a short questionnaire (see Appendix 2). The hood is terminally cleaned with 10% sodium hypochlorite followed by 70% ethanol. The hood area is then lined with clean lab mats. Thirty cubic centimeter (ccs) saline aliquots are poured into 50 ml centrifuge tubes and 1 cm³ of stool is distributed in these aliquot containers. The stool is mixed gently using a tongue depressor until a smooth suspension is formed. The contents are then filtered using a standard Parapak filter. The suspension is allowed to settle in the 50-ml centrifuge tube for 10 minutes and then poured off into a sterile container. This filtrate is then drawn up in 60 cc syringes, and labeled "For Enteral Use Only". Syringes are placed into sealed biohazard labeled bags for transport.

3.6. b) Fecal Microbiota Transplant (FMT) Procedure

Subjects will be asked to clean out their pouch using two over the counter enemas no longer than 3 hours before the procedure time. This is standard of care for patients undergoing routine flexible sigmoidoscopy. Subjects will also be asked to take 4 mg of loperamide (over-the-counter anti-diarrheal medication) one half hour before the FMT.

Subjects will be placed in the left lateral decubitus position with elevated hips in a designated private room in clinic or endoscopy suite for 90 minutes of FMT intervention. Subjects will be asked to rotate 180 degrees slowly during a 10-minute period. Subjects will be monitored for 30 minutes after FMT for any adverse events and discharged.

Concomitant Medications: Permitted concomitant medications: Patients may remain on chronic medications during the study period.

Prohibited medications: Patients will need to be off antibiotics and probiotics for at least 48 hours prior to fecal transplant.

End of the study: The end of study for each patient is defined as the date of the last visit (i.e. 3 month visit post-transplant).

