12. CLINICAL ADVERSE EVENTS

FMT in UC-associated Pouchitis

Version 3.0, date finalized 06/26/2017

An adverse event is any untoward medical occurrence in a subject administered the study procedure and which does not necessarily have a causal relationship with the study procedure. An adverse event can thus be any unfavorable and unintended sign, symptom, or disease temporally associated with the use of the study drug, whether or not considered related to the study drug. Pre-existing conditions that worsen during the study are considered adverse events. For the purposes of this study, AE's related to study procedures will be collected.

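### Section 7 omits the risk of the required antibiotic and probiotic stop, and sections 12 and 12.2 give a flare before FMT no sure route into the safety result

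*Combined protocol and SAP*

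**What the plan says.** - **Population.** Section 1 aims the trial at "chronic antibiotic-dependent pouchitis (CADP) and chronic antibiotic refractory pouchitis (CARP").
- **Objective.** Section 3.1 gives the primary objective: "To determine the safety and tolerability of fecal microbiota transplant (FMT) in treatment of chronic pouchitis".
- **Required stop.** Section 3.6 b: "Patients will need to be off antibiotics and probiotics for at least 48 hours prior to fecal transplant". It gives a minimum and no maximum. The same section also says "Patients may remain on chronic medications during the study period", without saying how this applies to a chronic antibiotic.
- **Stated risks.** Section 7: "The risks of this study are limited to those inherent with mucosal tissue biopsy and fecal microbial transplant with use of a flexible sigmoidoscopy". It goes on to describe bleeding, perforation, blood draws, transmission of infection, immune stimulation and discomfort. Stopping antibiotics or probiotics is not mentioned.
- **Adverse events.** Section 12 opens: "An adverse event is any untoward medical occurrence in a subject administered the study procedure". It then counts as an adverse event any condition already present that gets worse in the course of the trial. It ends by limiting collection to events related to study procedures.
- **Relatedness.** Section 12.2 has four categories, all defined by relation to FMT.
- **Size.** Section 6 plans 11 patients.

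**The concern.** A patient whose pouchitis is held in check by antibiotics may lose that control when the protocol requires the antibiotic to be stopped. This is a foreseeable harm of taking part, and it can occur before any donor stool is given. Section 7 words its risk list as complete and leaves this harm out.

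The adverse event rules add to the problem, because they are built around FMT. If a flare during the stop is not recorded, or is recorded only when the subject goes on to transplant, the result for the primary objective describes FMT alone and not what subjects undergo to receive it. With so few subjects, one missing event changes the reported proportion visibly.

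**Working it through.** The plan has no figure to reproduce on this point. Section 9 gives no power calculation, and no section gives a flare rate. The check is mainly a reading of the text, following one hypothetical subject who consents at screening, stops an antibiotic as required, and flares before FMT.

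1. **Is the risk listed?** No. Section 7 does not mention the stop, although section 3.6 b requires it.
2. **Is the flare an adverse event?** Section 12 supports both answers. Its opening sentence needs "any untoward medical occurrence in a subject administered the study procedure". If that means FMT, this subject does not qualify. The clause on worsening conditions would include the flare. If the study procedure means any scheduled procedure, the screening examination and blood draw already qualify the subject. The term is not defined.
3. **Is it collected?** Only if it is related to a study procedure. The stop is not a row in Table 2, but it is described in a subsection of section 3.6, which is headed as study procedures. No start of collection is given.
4. **How is it rated?** Under section 12.2, Probable and Possible both require a reasonable time sequence from FMT. An event before FMT cannot meet that, so only Remote or Unrelated remains. No category attributes an event to the stop.
5. **Is it reported if FMT never happens?** Section 3.6 treats the enrollment visit as the transplant visit. A subject who drops out before it may not be among the 11, and no reporting rule covers such subjects.
6. **Is there another trace?** Table 2 scores the clinical mPDAI at screening and the mPDAI at enrollment, so worsening could be seen in a subject who attends both visits. Section 9 plans no safety analysis of that change.

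**Scale of one event** (exact 95% limits, n = 11 from section 6):
- 0/11 = 0% (0 to 28.5%)
- 1/11 = 9.1% (0.2 to 41.3%)
- 2/11 = 18.2% (2.3 to 51.8%)

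If the subject never receives FMT and is not one of the 11, the comparison is 0/11 with 1/12 = 8.3%.

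**Expected number of flares** (assumed inputs only). Suppose 4 to 8 subjects are antibiotic-dependent and 1% to 30% of them flare on the stop. The expected count runs from 4 × 0.01 = 0.04 to 8 × 0.30 = 2.4. The chance of at least one runs from 1 − 0.99^4 = 3.9% to 1 − 0.70^8 = 94%. The range is too wide to say how many events would be missed.

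**The case against.** The strongest reply is that the text does not exclude such a flare. The clause on worsening conditions fits a pouchitis flare in a pouchitis patient. The serious event criteria in section 12.3 are not confined to the time after FMT and include hospitalization, and section 11 has the committee meet when a serious event is reported. The stop is described under section 3.6 and can be read as a study procedure. All of this stands. A reader might infer that a flare before FMT falls outside the adverse event definition, or that a hospitalized subject would have no serious event on record. The documents do not support either statement. They support only that such a flare may go uncounted.

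The reply also limits the exposure. The stop affects only subjects taking antibiotics or probiotics, the inclusion criteria in section 3.7 do not require antibiotic dependence, and both patient categories described there already have symptoms. That stands too, and the number at risk is unknown.

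A reader might also set an assumed flare rate against section 7's bleeding rate of 1 in 1,000 and call the omitted risk many times larger. No such ratio is claimed: the flare rate would be invented, and a flare of any severity is not comparable with significant bleeding.

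Section 7's opening sentence may be only loose drafting, since the section itself goes on to blood-draw risks. Adding loperamide or sedation to the list would complete it but change no result. The reply does not answer the silence on the stop, the undefined study procedure, the missing start of collection, or a relatedness scale tied to FMT alone.

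**Conclusion.** The point holds in a limited form. Section 7 leaves out the risk of a stop that the protocol itself requires, in a trial aimed partly at antibiotic-dependent patients. Section 12 is inconsistent on whether a flare before FMT is an adverse event. Together with section 12.2, it leaves such a flare without a dependable route into the safety result, particularly for a subject who never receives FMT. Serious events could still be captured under section 12.3.

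Each uncounted event among 11 subjects is worth 9.1 percentage points. How many there would be cannot be estimated from the documents. The conclusion assumes that some enrolled subjects are taking antibiotics or probiotics when the stop applies, which the aims make likely but the eligibility criteria do not guarantee. It should be corrected because it affects what is collected for the primary objective.

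**What to change.** Reconcile sections 3.6 b, 7, 12 and 12.2 as follows:

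1. In section 7, drop the wording that limits the risks, and name the required antibiotic and probiotic stop among them.
2. In section 12, define the study procedure so that it includes the stop, and record adverse and serious adverse events from the first protocol-required act.
3. In section 12.2, allow attribution to study requirements other than FMT.
4. Report events before FMT separately, including those in subjects who are never transplanted, with the denominator stated.

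The cost is some protocol wording, a few more adverse event records and possibly a higher reported event count. The antibiotic rule itself is left as it is. How the allowance for chronic medications applies to chronic antibiotics is for the sponsor to clarify. The consent form is not in the review copy, so nothing is said here about its content; it should be checked for consistency with the revised section 7.

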9. DATA ANALYSIS

Patients will be identified by physicians on this protocol in The Emory Clinic or Emory

FMT in UC-associated Pouchitis

Version 3.0, date finalized 06/26/2017

University Hospital. Patients will be consented using an IRB approved informed consent and undergo the procedure on their follow up visit.

Since this is a pilot study, no formal power calculation is provided. Descriptive statistics and ANOVA will be used to detect differences between groups. One-sample t-test or Wilcoxon's signed rank-tests will be used to see if there were any significant changes in PDAI and QOL scores before and after transplant. A Simon's two stage design will be used to decide whether to enroll more patients in the future.

Data relating to laboratory results will be obtained through the EMR computerized patient information systems EML microbiological reports. A dataset will be created in a secure file, with access given only to authorized study staff.

A list of possible cases that have been reviewed for inclusion will be secured by study staff. This list will contain subject name, birth date, medical record number, and the number of the corresponding data abstraction sheet. Such a list will be maintained so as not to duplicate the abstraction of a single subject. Once the data from all included subjects is entered into a database, the list of identifiable patient information will be destroyed.

Data analysis will be performed with Microsoft Excel, SAS Institute software, and SPSS software.

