10. ENDPOINTS

The primary endpoint of this study will be resolution of clinical pouchitis symptoms using the clinical component of the modified pouchitis disease activity index without relapse for 3 months. Secondary endpoints include 16S ribosomal gene sequencing and metabolomic profiles that are more favorable (as defined by the donor microbiota). An additional secondary endpoint will be improvement of quality of life as determined by QOL questionnaires.

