12.2 Determination of Relationship of Adverse Event to FMT

There will be four categories of possible relationship between the adverse event and FMT. Determination of drug-relatedness of the adverse event to FMT will be determined by the investigator.

Category 1: Probable (must have first three)

A probable relationship will be assigned to an adverse event that is considered, with a high degree of certainty, to be related to FMT. An adverse event may be considered probable if:

1. It follows a reasonable temporal sequence from administration of the FMT.
2. It cannot be reasonably explained by the known characteristics of the subject's clinical state, environmental or toxic factors, or other modes of therapy administered to the subject.
4. It follows a known pattern of response to FMT

Category 2: Possible (must have first two)

A possible relationship will be assigned to an adverse event when the connection with FMT administration appears unlikely but cannot be ruled out with certainty. An adverse event will be considered possible if:

1. It follows a reasonable temporal sequence from administration of FMT
2. It may have been produced by the subject's clinical state, environmental or toxic factors, or other modes of therapy administered to the subject
3. It follows a known pattern of response to FMT

Category 3: Remote (must have first two)

FMT in UC-associated Pouchitis

Version 3.0, date finalized 06/26/2017

An adverse event will be considered remote if:

1. It does not follow a reasonable temporal sequence from administration of FMT
2. It may readily have been produced by the subject's clinical state, environmental or toxic factors, or other modes of therapy administered to the subject.
3. It does not follow a known pattern of response to FMT

Category 4: Unrelated

An adverse event will be considered unrelated if it is judged to be clearly and incontrovertibly due only to extraneous causes such as disease, environment, etc. while not meeting the criteria for drug relationship as listed above for remote, possible, or probable.

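### The plan can under-count deterioration after FMT: no specified output reports how many subjects worsen, and adverse-event collection is limited to procedure-related events

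*Combined protocol and SAP*

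**What the plan says.** Section 3.1 makes safety and tolerability of FMT the primary objective. Section 7 states: "The primary risks of fecal microbiota transplantation are transmission of infection and potential immune stimulation".

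The primary endpoint in section 10 is an efficacy outcome: "resolution of clinical pouchitis symptoms using the clinical component of the modified pouchitis disease activity index without relapse for 3 months". No significance test is specified for it. Section 9 adds descriptive statistics, and a one-sample t-test or signed-rank test "to see if there were any significant changes in PDAI and QOL scores before and after transplant". It names a Simon two-stage design for deciding on future enrollment, without parameters, and says "Since this is a pilot study, no formal power calculation is provided". Section 6 sets the size: "A total of 11 patients with IPAA/UC related pouchitis will be enrolled over 12 months as part of this pilot study".

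Section 12 defines an adverse event broadly. Causality is not required, and a pre-existing condition that gets worse during the study counts. The last sentence of the same paragraph then narrows collection: "AE's related to study procedures will be collected". Section 11 has a two-physician committee review the adverse events every 6 months, or urgently after a reported SAE.

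Table 2 schedules the clinical part of the mPDAI at screening, week 2, week 4 and 3 months, and the mPDAI at enrollment.

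**The concern.** For a trial whose first question is safety, the reader will want to know how many treated subjects were worse afterwards. The documents define no deterioration outcome and commit to no count of it.

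Three routes could show deterioration, and each is incomplete. The primary endpoint puts worse and unchanged subjects together as non-resolvers. The tests of change summarise the group and do not say who worsened. The adverse-event route starts from a definition that includes worsening, then applies a collection limit under which a flare judged to be the underlying disease can be left out.

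At stake is a safety summary that understates worsening even though the trial already holds the scores that would show it.

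**Working it through.** **1. The plan's own figure.** The only design figure is n = 11. It comes with no power calculation, error rates, response rates or Simon parameters, so it can be neither reproduced nor refuted.

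**2. Inputs.** n = 11, single arm (sections 3 and 6). The clinical score runs from 0 to 6, since the item maxima in Appendix 1 are 2 + 1 + 2 + 1. Table 2 schedules no sigmoidoscopy or biopsy after enrollment, so change after FMT can be assessed on the clinical part only. Assumptions of mine: two-sided 0.05 (the plan gives no level), and illustrative data in which all 11 start at 3, 8 fall to 0 and stay there, and the other 3 change by 0, +1, +2 or +3.

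**3. What each planned summary shows.** The t statistic is mean / (SD/√11) on 10 df. For three subjects at +2:
- mean = (8 × (−3) + 3 × 2)/11 = −18/11 = −1.64
- sum of squared deviations = (8 × 9 + 3 × 4) − 18²/11 = 84 − 29.45 = 54.55
- SD = √(54.55/10) = 2.34
- t = −1.64/(2.34/√11) = −2.32, p = 0.0425

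The other rows follow in the same way. The signed-rank p-values are exact, with zeros dropped and mid-ranks for ties.

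| Other 3 subjects | Resolved | Mean change | t-test p | Signed-rank p |
|---|---|---|---|---|
| 0 | 8/11 | −2.18 | 0.0004 | 0.008 |
| +1 | 8/11 | −1.91 | 0.007 | 0.008 |
| +2 | 8/11 | −1.64 | 0.0425 | 0.008 |
| +3 | 8/11 | −1.36 | 0.138 | 0.227 |

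The primary endpoint is 8/11 (73%, exact 95% CI 39% to 94%) in every row. The t-test does respond to worsening. The signed-rank p is the same in the first three rows because zeros are dropped and the changes are tied.

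**4. How special the example is.** With 11 distinct non-zero changes, the signed-rank test is significant if the ranks of the worsened subjects sum to 10 or less (p = 0.042; a sum of 11 gives 0.054).
- 3/11 worse: p runs from 0.0137 to 0.83, and 11 of 165 rank patterns are significant.
- 4/11 worse: 1 of 330 is significant.
- 5/11 worse: none is.

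Significant improvement with about a quarter worse is therefore possible, but only if the worsening is small relative to the improvements.

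**5. What a count would show.** The Clopper-Pearson 95% interval for 3/11 is 6.0% to 61.0%. For 0/11 the upper limit is 1 − 0.025^(1/11) = 28.5%.

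**6. The adverse-event route, side by side.** Section 12 first makes worsening of an existing condition an adverse event whatever its cause, then collects only events related to study procedures. Section 12.2 has the investigator grade relatedness to FMT, with Remote and Unrelated among the four categories. Those two categories would have little to hold if unrelated events were not collected. On the collection sentence as written, a flare attributed to chronic pouchitis need not be recorded, and the committee can review only what is recorded.

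**The case against.** The strongest objection is that the tests in section 9 already penalise worsening. That stands. A reader might infer that the planned analyses as a whole score a worse subject as unchanged, and that this is how a significant improvement could hide harm. The documents do not support that. Only the binary endpoint merges the two states, and it has no significance test. The tests that could give significance count worsening against improvement, and three subjects at +3 remove it. What remains is that a p-value or mean is not a count.

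A reader might also infer that immune stimulation would appear as a pouchitis flare. Section 7 does not say how it would present, and the point here does not need that link.

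A third tempting reading is that section 12.2 shuts flares out, because Probable requires of an event that "It cannot be reasonably explained by the known characteristics of the subject's clinical state". But Possible expressly allows for events that the clinical state may have produced, and a flare in reasonable temporal sequence to FMT fits it. Being kept from Probable is not being graded unrelated. Waiving that criterion in a single-arm study would also be a debatable trade.

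Two further points stand in part. Serious events have their own route through sections 11, 12.3 and 12.4, so the gap mainly concerns non-serious worsening. And the descriptive statistics in section 9 could include a worsening count, though nothing commits to one.

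Finally, worsening need not be due to FMT. Section 1 targets antibiotic-dependent as well as refractory disease, section 3.6 b requires antibiotics to be stopped at least 48 hours beforehand, and there is no control arm. That limits how a count can be interpreted. It also means attribution of individual flares is uncertain, which is a reason not to make collection depend on it.

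**Conclusion.** The concern holds in a limited form. On the primary objective, the plan can under-count deterioration: the primary endpoint does not show it, the tests of change give no number of subjects who worsen, and the collection sentence in section 12 conflicts with the definition just before it. In the illustration, 3/11 worse (27%, exact 95% CI 6% to 61%) coexists with t-test p = 0.0425; with slightly larger worsening (+3) the p-value is 0.14.

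The change scores, the common baseline of 3, reading resolution as a score of 0, and the two-sided 0.05 level are assumptions. The gap in section 12 rests on the text alone. None of this shows that FMT causes worsening, or that a favourable result would be wrong. It shows that the planned output could leave the matter unreported.

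**What to change.** **Section 12.** Reconcile the definition with the collection sentence, so that worsening of pouchitis after FMT is recorded as an adverse event whatever its attribution. Relatedness would still be graded under section 12.2 as written.

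**Sections 9 and 10.** Add deterioration as a safety outcome. For week 2, week 4 and month 3, report the number and percentage of FMT recipients whose clinical mPDAI is above their enrollment score, with exact 95% CIs, the number assessed at each visit, and a by-subject listing. Even a count of 0/11 should carry its upper limit of 28.5%.

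**Cost.** A few sentences and one table, from scores already scheduled. With no control arm, natural and antibiotic-withdrawal flares will be included, so tolerability may look slightly less favourable, and the report should say so beside the table.
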